7.1 Derivation

The items that need to be calculated in this study are as follows, but the following matters may be considered.

- If an additional calculated variable related to the variables defined below is required during statistical analysis, SAP may not be revised, but the variable will be specified in TLFs.
- Depending on the data actually collected, the item units defined in SAP may change (Ex. duration of disease: months → years)

Age

- If the birthday has passed from the date of signing the consent form: (Year of signing the consent form – Year of birth)
- If the birthday has not passed since the date of signing the consent form: (Year of signing consent – Year of birth – 1)

Duration of disease (days)

- (Start date of initial dose of this drug – Date of diagnosis + 1)
- For continuous analysis, if the date is not complete, it is excluded from the analysis.
- For categorical analysis, if the diagnosis date is partially collected, it is analyzed according to the following rules.
 - If 'day' of the diagnosis date is missing: (Year & month of the start date of initial dose of this drug – Year & month of diagnosis date)
 - If there is only 'year' in the diagnosis date: (Year of the start date of initial dose of this drug – Year of the diagnosis date)

Total administration period of this drug (days)

- $\sum_{i=1}^n [(End\ date\ of\ drug)_i - (Start\ date\ of\ drug)_i + 1]$,
i: The i^{th} administration period of the subject in the n times of administration period of this drug
- If the end date of the i^{th} dose is "in progress" or is missing, other than the end date of the last dose:
 - [(one day before start date of $i+1^{th}$ dose) – (dose start date) + 1]
- If the end date of the last dose is 'in progress' or missing, it is substituted in the following order.
 - [(Date of Last visit) – (Start date of drug) + 1]
 - [(Start date of drug) – (Start date of drug) + 1]

Total dose of this drug (empagliflozin/metformin)(mg)

- $\sum_{i=1}^n [(End\ date\ of\ drug)_i - (Start\ date\ of\ drug)_i + 1] * Daily\ dose$
i: The i^{th} administration dose of the subject in the n times of administration dose of this drug

Average of daily dose drug (empagliflozin/metformin)(mg/day)

- Total dose(mg) / Total administration period (days)

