5.5 Other Statistical Considerations

The analysis will be conducted in consideration of the following matters, and if separate considerations are needed depending on the analysis item, the contents will be described in the relevant item of '7.1 Derivation'.

- The standard for converting Day into Month or Year is as follows: 1 month = 30.4375 days, 1 year = 365.25 days
- For all data analyses, the test statistic is a two-sided test, and the statistical significance level is based on 0.05.
- When calculating percentages from categorical demographics and baseline data, the denominator is defined as the sum of the number of subjects in each category. However, for analysis by detailed medical history/medication type, the denominator is defined as the number of subjects with medical history/medication.
- When calculating percentages of the incidence of adverse events and valid/invalid by demographics and baseline data, the denominator is defined as the number of subjects in each category. However, upon analyzing by detailed medical history/medication type, the denominator is defined as the number of subjects with medical history/medication in each category.
- When calculating the percentage of the incidence for each type of adverse event, the denominator for analyzing the safety analysis set is defined as the number of subjects in the safety analysis set. However, in the analysis of subjects excluded from safety evaluation, the denominator is defined as the number of subjects excluding those who were investigated in duplicate, those who did not receive this drug, or those who did not undergo follow-up for safety.

- In categorical data, if the cells with an expected frequency of less than 5 are more than 20% of all cells in the between group test, Fisher's exact test is used for analysis instead of the Chi-square test.
- For the confidence interval, a 95% two-sided confidence interval is calculated by applying the exact confidence interval method.
- If the total number of adverse events is 10 or less, the analysis of the incidence of adverse events by demographics and baseline data can be replaced with the list of adverse events.
- Multiple logistic regression analysis is not performed when there are two or less variables that show significant differences in the analysis of the incidence of adverse events by demographics and baseline data.

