7.2 Categorization

The categories for each item for categorical analysis are as follows. However, categories defined for categorical analysis of continuous data may be added or changed according to the distribution of the actually collected data.

Items	Category
• Children	< 19 years, ≥ 19 years
• Elderly	< 65 years, ≥ 65 years
• Pregnancy	Yes, No, Not Applicable
• Renal impairment	Yes, No
• Hepatic impairment	Yes, No
• Long-term follow-up	< 24 weeks,

Items	Category
	≥ 24 weeks
• Age	19 years ~ 29 years, 30 years ~ 39 years, 40 years ~ 49 years, 50 years ~ 59 years, ≥ 60 years
• Gender	Male, Female
• Smoking status	Never smoked, Ex-smoker, Currently smokes
• Family history of T2DM	Yes, No
• Disease period	< 1 year, 1 year ~ < 5 years, 5 years ~ < 10 years, ≥ 10 years
• Diabetes mellitus complications	Retinopathy, Neuropathy, Nephropathy, Vasculopathy, Etc.
• Medical history	Yes, No
• Allergy	Yes, No
• Renal failure	Yes, No
• Total administration period of JardianceDuo	< 12 weeks, 12 weeks ~ ≥ 24 weeks, ≥ 24 weeks
• Average of daily dose (Empagliflozin)	< 10 mg, 10 mg ~ ≥ 25 mg, ≥ 25 mg
• Average of daily dose (Metformin)	< 1,000 mg, 1,000 mg ~ ≥ 1,700 mg, 1,700 mg ~ ≥ 2,000 mg, ≥ 2,000 mg
• Other anti-diabetic agent	Yes, No
• Concomitant medications	Yes, No
• Discontinuation of study medication	Yes, No
• Severity	Mild, Moderate, Severe
• Serious AE	Yes, No
• SAE Category	Results in death, Immediately life-threatening, Persistent or significant disability/ incapacity, Requires patient hospitalization, Prolongs patient hospitalization, Congenital anomaly/ birth defect, Other comparable medical criteria
• Action taken	Continue, Reduced, Discontinued, Increased, discontinued and reintroduced, Unknown, Not applicable
• Recurrence according to reintroduced	Recurrence, No-recurrence, Unknown,

Items	Category
	Not applicable
• Causality	Certain, Probable/Likely, Possible, Unlikely, Conditional / Unclassified, Unassessable / Unclassifiable
• Factors other than JARDIANCE DUO	None, Concomitant medication, Concomitant diagnoses, Other
• Outcome	Recovered, Not yet recovered, Sequelae, Fatal, Unknown
• Therapy for the event	Yes, No
• Effectiveness	Effectiveness, Ineffectiveness

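### Partial diabetes diagnosis dates are dropped from the mean duration but kept in the duration bands, where year-only dates can only move a patient to a higher band (minor)

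*SAP*

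**What the plan says.** SAP 6.4 reports duration of disease both as a continuous and as a categorical variable. SAP 7.1 gives the derivation:

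- **Complete date:** "Start date of initial dose of this drug – Date of diagnosis + 1", in days. SAP 5.5 sets the conversion as "1 month = 30.4375 days, 1 year = 365.25 days".
- **Incomplete date, continuous summary:** "For continuous analysis, if the date is not complete, it is excluded from the analysis".
- **Incomplete date, bands, only the day missing:** year and month of diagnosis are subtracted from year and month of first dose.
- **Incomplete date, bands, only the year known:** "Year of the start date of initial dose of this drug – Year of the diagnosis date".

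SAP 7.2 sets the bands at "< 1 year, 1 year ~ < 5 years, 5 years ~ < 10 years, ≥ 10 years".

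SAP 5.4 leaves missing data unreplaced and excludes partial dates that cannot be calculated, but defers to 7.1 where an item needs its own handling. Protocol 8.7.5 says that all available data will be used. Neither document states an expected share of partial dates, asks for that share to be reported as such, or plans a sensitivity analysis.

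**The concern.** The two halves of one baseline table rest on different patients and different arithmetic. A patient whose diagnosis year is known counts in the bands but not in the mean, standard deviation, median or range. Excluding a known year also sits badly with protocol 8.7.5, although that sentence does not expressly require imputation.

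The year-only rule has a second defect. Two calendar years can differ by one when only days have passed, so the rule rounds in one direction at each cut point.

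Duration is not an endpoint. Disease period is, however, a listed baseline parameter (protocol 8.7.1), and adverse event occurrence is tested by baseline category (protocol 8.7.2, SAP 5.5). It may also enter the comparison of baseline characteristics with TRAJENTA DUO in protocol 8.7.1.

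**Working it through.** The plan gives no figure for duration or for partial dates, and the sample size of 600 is a regulatory number, so there is no planned figure to reproduce.

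**1. Direction of the year-only rule.** The calendar-year difference equals completed years or completed years plus one.

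| Diagnosis | First dose | True years | Year difference | Band assigned |
|---|---|---|---|---|
| 31 Dec 2018 | 2 Jan 2019 | 3/365.25 = 0.008 | 1 | 1 to under 5 (true: under 1) |
| 15 Dec 2014 | 10 Jan 2019 | 4.07 | 5 | 5 to under 10 (true: 1 to under 5) |
| 15 Dec 2009 | 10 Jan 2019 | 9.07 | 10 | 10 and over (true: 5 to under 10) |
| 5 Jan 2014 | 20 Dec 2019 | 5.96 | 5 | 5 to under 10 (correct) |

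**2. How often at a cut point.** Inputs: data collection from 30 Jan 2018 to 11 Aug 2020 (protocol section 5). Subtracting 24 weeks puts the last baseline near 25 Feb 2020. Assumption: the diagnosis day is uniform within its calendar year.

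If first dose falls a fraction f through the year, a patient whose year difference equals the cut lies truly below it with probability about 1 − f. Averaging f over the window, by calendar year:

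(336 × 0.541 + 365 × 0.501 + 56 × 0.078) / 757 = 0.488, so 1 − f ≈ 0.51.

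Day-by-day enumeration gives 51.2% at 1 and 5 years and 51.1% at 10 years. Misplacement downward is 0% at all three cuts.

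**3. Net band shift and bias of the mean.** Simulation of 1,000,000 patients per setting. Assumptions, none from the documents: gamma durations (shape 1.2, capped at 40 years) with mean about 5, 8 or 10 years; every partial date is year-only; the share partial at under 5 / 5 to under 10 / 10 years and over is as shown. Ranges run across the three means.

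| Pattern of partial dates | Overall share | Mean bias (years) | Under 1 year (points) | 10 years and over (points) |
|---|---|---|---|---|
| Flat 30% | 30% | 0.0 | −1.1 to −2.3 | +0.5 to +0.7 |
| Rising, 10/30/50% | 20-30% | −0.7 to −1.7 | −0.4 to −0.8 | +0.5 to +0.7 |
| Rising, 5/20/60% | 16-30% | −0.9 to −2.5 | −0.2 to −0.4 | +0.3 to +0.4 |
| Falling, 40/20/10% | 23-31% | +0.7 to +1.1 | −1.5 to −3.1 | +0.3 to +0.4 |

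If all 600 patients were analysed, the under-1-year shift would be about 1 to 18 patients (600 × 0.002 to 600 × 0.031) and the top-band shift about 2 to 4. The mean would lose 94 to 187 patients.

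**4. Upper limit for the bands.** If every date were year-only, the under-1-year band would fall from 14.3% to 6.6%, 8.6% to 3.9%, or 6.7% to 3.0% (means 5, 8, 10). The top band would rise from 12.6% to 14.1%, 28.9% to 31.0%, or 37.9% to 40.1%.

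**5. Day-missing dates.** The error is about a month at most. If every date lacked only the day, the under-1-year band would fall by 0.3 to 0.6 points.

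**6. One midpoint rule for both summaries.** Treating year-only dates as 1 July, capped at first dose, gives a mean bias within 0.002 years and net band shifts of at most 0.24 points in every setting. Part of this follows from simulating diagnosis days evenly over the year.

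**The case against.** The strongest defence is that the rule is prespecified, follows the general policy in SAP 5.4, and concerns a descriptor only. SAP 5.3 requires the number of subjects with each continuous summary and frequencies with each categorical one, so a reader can see how many patients are in the bands but not in the mean. At plausible partial-date shares the bands move little. All of this stands and keeps the point minor. It does not explain why one variable needs two rules, nor does it remove the one-directional misbanding.

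Three stronger readings are tempting, and the documents do not support them:

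- **That all the bands use bare calendar years.** They do so only for year-only dates; complete and day-missing dates are handled closely.
- **That the mean is too low while the bands are too high.** The downward bias needs partial dates to become commoner with duration. That is plausible, but the documents do not say so. The two effects also do not peak together: the largest under-1-year shift (−3.1 points) arises under the falling pattern, which biases the mean up, while the rising patterns give at most −0.8 points.
- **That the rule would by itself distort the TRAJENTA DUO comparison.** Under the rising patterns the bias is 0.16 to 0.29 standard deviations, above the protocol's 10% threshold. But the documents do not say whether duration enters as a mean or as bands, or how the comparator study derived it. If both used the same rule, the bias would tend to cancel.

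**Conclusion.** The point holds, at minor importance. Two parts need no assumption about why dates are partial: the continuous summary and the bands describe different patients, and year-only dates are misbanded upward only. The figure of about half at each cut assumes diagnosis days spread evenly over the year.

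The net band shifts (0.2-3.1 points down for under 1 year, 0.3-0.7 up for 10 years and over) rest on assumed duration distributions and on partial-date shares of about 16-31%, all taken as year-only. The bias of the mean is conditional in both size and sign: about −0.7 to −2.5 years if partial dates rise with duration, zero with no link, and +0.7 to +1.1 years if they fall. No endpoint is affected. The baseline duration table and adverse event incidence by duration are.

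**What to change.** Replace the partial-date rules for duration in SAP 7.1 by one rule serving both summaries: a missing day is set to the 15th; a missing day and month are set to 1 July; the imputed date is capped at the first-dose date. Compute duration from that date with the existing formula and use it for both the continuous summary and the bands. Footnote the number of patients imputed, split by day-missing and year-only. If duration enters the TRAJENTA DUO comparison, apply the same rule to both data sets where the dates allow.

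The cost is a few SAP lines and a small programming change, and SAP 5.4 already allows item-specific handling in 7.1. The downside is up to about 6 months of error for each year-only patient. Individual patients can still be misbanded, but no longer in one direction only.

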7.2 Categorization

The categories for each item for categorical analysis are as follows. However, categories defined for categorical analysis of continuous data may be added or changed according to the distribution of the actually collected data.

Items	Category
• Children	< 19 years, ≥ 19 years
• Elderly	< 65 years, ≥ 65 years
• Pregnancy	Yes, No, Not Applicable
• Renal impairment	Yes, No
• Hepatic impairment	Yes, No
• Long-term follow-up	< 24 weeks,

Items	Category
	≥ 24 weeks
• Age	19 years ~ 29 years, 30 years ~ 39 years, 40 years ~ 49 years, 50 years ~ 59 years, ≥ 60 years
• Gender	Male, Female
• Smoking status	Never smoked, Ex-smoker, Currently smokes
• Family history of T2DM	Yes, No
• Disease period	< 1 year, 1 year ~ < 5 years, 5 years ~ < 10 years, ≥ 10 years
• Diabetes mellitus complications	Retinopathy, Neuropathy, Nephropathy, Vasculopathy, Etc.
• Medical history	Yes, No
• Allergy	Yes, No
• Renal failure	Yes, No
• Total administration period of JardianceDuo	< 12 weeks, 12 weeks ~ ≥ 24 weeks, ≥ 24 weeks
• Average of daily dose (Empagliflozin)	< 10 mg, 10 mg ~ ≥ 25 mg, ≥ 25 mg
• Average of daily dose (Metformin)	< 1,000 mg, 1,000 mg ~ ≥ 1,700 mg, 1,700 mg ~ ≥ 2,000 mg, ≥ 2,000 mg
• Other anti-diabetic agent	Yes, No
• Concomitant medications	Yes, No
• Discontinuation of study medication	Yes, No
• Severity	Mild, Moderate, Severe
• Serious AE	Yes, No
• SAE Category	Results in death, Immediately life-threatening, Persistent or significant disability/ incapacity, Requires patient hospitalization, Prolongs patient hospitalization, Congenital anomaly/ birth defect, Other comparable medical criteria
• Action taken	Continue, Reduced, Discontinued, Increased, discontinued and reintroduced, Unknown, Not applicable
• Recurrence according to reintroduced	Recurrence, No-recurrence, Unknown,

Items	Category
	Not applicable
• Causality	Certain, Probable/Likely, Possible, Unlikely, Conditional / Unclassified, Unassessable / Unclassifiable
• Factors other than JARDIANCE DUO	None, Concomitant medication, Concomitant diagnoses, Other
• Outcome	Recovered, Not yet recovered, Sequelae, Fatal, Unknown
• Therapy for the event	Yes, No
• Effectiveness	Effectiveness, Ineffectiveness

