#### 8.1.2 Dosage and Administration

The recommended dose is one tablet twice daily. The dosage should be individualised on the basis of the patient's current regimen, effectiveness, and tolerability while not exceeding the maximum recommended daily dose of 25 mg of empagliflozin and 2000 mg of metformin.

- In patients not adequately controlled on metformin alone or in combination with other products, including insulin, the recommended starting dose of JARDIANCE DUO® should provide empagliflozin 5 mg twice daily (10 mg total daily dose) and the dose of metformin similar to the dose already being taken. In patients tolerating a total daily dose of empagliflozin 10 mg and requiring additional glycaemic control, the dose can be increased to a total daily dose of empagliflozin 25 mg.

- Patients switching from separate tablets of empagliflozin (10 mg or 25 mg total daily dose) and metformin to JARDIANCE DUO® should receive the same daily dose of empagliflozin and metformin already being taken.

When JARDIANCE DUO® is used in combination with a sulphonylurea and/or insulin, a lower dose of sulphonylurea and/or insulin may be required to reduce the risk of hypoglycaemia (see section on 4. Adverse Events and 6. Interactions on the [13.4 Korean label](#)).

JARDIANCE DUO® should be given with meals to reduce the gastrointestinal undesirable effects associated with metformin.

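### SAP 7.2 prints overlapping classes for average daily dose and administration period; as written they would distort the exposure table and the exploratory adverse-event comparisons by dose or duration

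*SAP*

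**What the plan says.** SAP 7.2 lists the categories for each categorical analysis. Three rows give a middle class an upper limit written with '≥':

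- Average daily empagliflozin dose: below 10 mg, then "10 mg ~ ≥ 25 mg, ≥ 25 mg".
- Average daily metformin dose: below 1,000 mg, then "1,000 mg ~ ≥ 1,700 mg, 1,700 mg ~ ≥ 2,000 mg, ≥ 2,000 mg".
- Total administration period: below 12 weeks, then "12 weeks ~ ≥ 24 weeks, ≥ 24 weeks".

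The disease-period row of the same table is written differently: "1 year ~ < 5 years, 5 years ~ < 10 years".

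These classes feed planned outputs. SAP 6.7 lists administration period and both average daily doses as categorical summaries. Protocol 8.7.1 places period of use and average daily dose among the demographic parameters, and Protocol 8.7.2 item 3 compares adverse-event occurrence across demographic data by chi-square or Fisher's exact test. For percentages of categorical demographic and baseline data, SAP 5.5 states that "the denominator is defined as the sum of the number of subjects in each category"; for adverse-event incidence by category, it uses the number of subjects in each category.

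**The concern.** A class that ends at 'at least 25 mg' and is followed by a class that starts at 'at least 25 mg' does not separate the two groups. This would matter little if few patients lay near the limits, but the limits are the label's own daily totals. Protocol 8.1.2 says "The recommended dose is one tablet twice daily", so a constant regimen lands on a cut point.

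Two things are at stake. The exposure table could misstate how many patients took the higher doses. The adverse-event comparison by dose or duration could set a group against a larger group that already contains it, which shrinks the contrast and breaks the assumption of exclusive groups behind chi-square and Fisher tests. SAP 5.5 also decides whether multiple logistic regression is run from the number of variables significant in these comparisons, so a distorted test can carry forward. The study's primary objective is safety.

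**Working it through.** The plan gives no calculated figure to reproduce here; 600 is a regulatory sample size. The check assigns the label regimens to the printed classes and follows the counts.

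**Inputs.** Tablet strengths are 5 or 12.5 mg empagliflozin with 500, 850 or 1,000 mg metformin (study title, Protocol section 4). Dosing is one tablet twice daily (Protocol 8.1.2). Average daily dose is total dose divided by total administration period (SAP 7.1), so a constant regimen averages exactly its daily total: 2 × 5 = 10 or 2 × 12.5 = 25 mg; 2 × 500 = 1,000, 2 × 850 = 1,700 or 2 × 1,000 = 2,000 mg.

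**Number of classes each value falls in**

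| Value | Literal '~ ≥' | Read as '~ ≤' | Read as '~ <' |
|---|---|---|---|
| 10 mg | 1 | 1 | 1 |
| 25 mg | 2 | 2 | 1 |
| 1,000 mg | 1 | 1 | 1 |
| 1,700 mg | 2 | 2 | 1 |
| 2,000 mg | 3 | 2 | 1 |
| 24 weeks exactly | 2 | 2 | 1 |
| More than 24 weeks | 2 | 1 | 1 |

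Only '~ <' gives a partition. If a program tests the literal limits in order and stops at the first match, no patient is counted twice, but everyone at 10 mg or more stops in the middle class and the top class is empty. In the metformin row both upper classes are empty.

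**Effect on percentages (literal limits).** Assume 600 patients, all at exactly 10 or 25 mg, with share s at 25 mg, and the sum-of-categories denominator. The counts are 600 and 600s, so the top class prints as s/(1 + s).

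| Assumed share at 25 mg | Sum of counts | Top class prints as |
|---|---|---|
| 10% | 660 | 9.1% |
| 25% | 750 | 20.0% |
| 50% | 900 | 33.3% |
| 75% | 1,050 | 42.9% |

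With metformin in equal thirds (assumed), the counts are 600 + 400 + 200 = 1,200, printed as 50.0/33.3/16.7% instead of 33.3% each. With 10/10/80% of patients in the three duration classes (assumed), the counts are 60 + 540 + 480 = 1,080, printed as 5.6/50.0/44.4%.

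**Effect on a two-class test.** Assume adverse-event rates of 20% at 10 mg and 30% at 25 mg. With p the pooled proportion, chi-square = (difference)² / [p(1 − p)(1/n₁ + 1/n₂)].

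- Half at 25 mg, disjoint: 60/300 against 90/300; p = 0.25; 0.10² / (0.25 × 0.75 × 2/300) = 8.00, P = 0.0047.
- Half at 25 mg, as printed: 150/600 against 90/300; p = 240/900 = 0.267; 0.05² / (0.267 × 0.733 × 0.005) = 2.56, P = 0.11.
- A quarter at 25 mg, disjoint: 90/450 against 45/150 gives 6.45, P = 0.011.
- A quarter at 25 mg, as printed: 135/600 against 45/150 gives 3.70, P = 0.054.

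In 20,000 simulated studies per scenario, rejection at the two-sided 0.05 level with no true difference (20% in both groups) fell from about 5% to 0.04% (half at 25 mg) or 1.1% (a quarter). With 20% against 30%, power fell from 81% to 26% (half) or from 71% to 48% (a quarter). The distortion runs towards missing a difference.

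**The case against.** The strongest reply is that this is a typographical slip which the table itself resolves. The disease-period row and the two-class rows for age and 24 weeks are disjoint. SAP 6.4, 6.5 and 6.8.2 say explicitly when one subject may appear in several categories, and 6.7 gives no such permission for dose or period. Class counts adding to more than the number of patients would be noticed, and SAP 7.2 lets categories of continuous data be changed. Much of this stands: the intended sign is almost certainly '<'. But the change clause only permits a repair, and ties it to the distribution of the data. Ordered logic, which avoids the visible double count, produces an empty top class instead.

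A reader might infer that patients on full label doses will be counted two or three times and that the dose results will therefore be wrong. The documents do not support that as fact. Double counting depends on literal programming. The variable is also an average over the whole administration period: Protocol 8.1.2 describes an increase from 10 to 25 mg in some patients, and a patient who changes during follow-up averages between those limits and falls in one empagliflozin class even as printed. The share at exactly 25 mg is not given anywhere.

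Two links are arguable. The sum-of-categories denominator is stated for demographic and baseline data; it reaches dose and period because Protocol 8.7.1 lists them there. The text of SAP 6.8.3 is not in the supplied SAP, so the comparison by dose or duration rests on Protocol 8.7.1 and 8.7.2 with SAP 5.5.

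A PDF reading error cannot be wholly excluded, but the same sign appears in all four places while '<' is read correctly in the same rows.

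**Conclusion.** The limits are wrong as written. Four middle classes in three rows of SAP 7.2 overlap the class above, against the table's own convention, and constant label regimens sit exactly on the cut points. Reading the sign as '≤' does not cure this for 25, 1,700 or 2,000 mg.

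The consequence is conditional: literal programming would count some patients more than once, and ordered programming would empty the upper classes. Both would distort the SAP 6.7 exposure breakdown and the exploratory adverse-event comparisons by dose or duration. The sizes above are illustrations that rest on assumed dose shares and event rates, not forecasts.

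The reach is limited. Overall adverse-event incidence with its confidence interval, the SAP 6.8.2 adverse-event tables for under 24 weeks and 24 weeks or more (which use disjoint classes), and the HbA1c change do not depend on these rows. It should be corrected, but it does not threaten the main results.

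**What to change.** In SAP 7.2, write the four middle classes as `12 weeks ~ < 24 weeks`, `10 mg ~ < 25 mg`, `1,000 mg ~ < 1,700 mg` and `1,700 mg ~ < 2,000 mg`, and add one sentence stating that the classes in these three rows are mutually exclusive. Every label regimen and every duration then falls in exactly one class, and the counts add to the number of patients with data. The cost is four signs and one sentence, best made before the tables are programmed. The change concerns analysis classes only and has no bearing on dosing.
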